Official Title of the study: **Effect of Varied Outreach Methods on Appointment Scheduling, Appointment Completion, and Receipt of COVID-19 Vaccination**

NCT number: **NCT04904744**

Document name: **Study Protocol**

Date of the document: **12/1/21**

Redesigning Outreach Post-COVID-19 in Academic Pediatric Primary Care

[name], MS
Professor of Pediatrics
Division Director
General & Community Pediatrics
Cincinnati Children's Hospital Medical Center
[name]
[name]
[contact]

[name], BSN, MSN
Clinical Manager
General & Community Pediatrics
Cincinnati Children's Hospital Medical Center
[name]
[name]
[contact]

[name], MHA
Associate Division Director, Primary Care
General & Community Pediatrics
Cincinnati Children's Hospital Medical Center
[name]
[name]
[contact]

[name]
Staff Physician 1
General & Community Pediatrics
Cincinnati Children's Hospital Medical Center
[name]
[name]
[contact]

[name], BA
Clinical Research Coordinator III
General & Community Pediatrics
Cincinnati Children's Hospital Medical Center
[name]
[name]
[contact]

[name]
Senior Biostatistician
General & Community Pediatrics
Cincinnati Children's Hospital Medical Center
[name]
[name]
[contact]

1. Objective

Our objective is to determine the effectiveness of varied outreach methods (e.g. automated reminder calls/text messages with or without personalized calls/texts, MyChart messaging) to children age 12-14 months, 4 years old, or 6-17 years old who are due for a WCC visit and don't have one scheduled in the next 45 days on the outcomes of appointment scheduling, appointment completion, and receipt of the MMR vaccination.

Background

The Cincinnati Children's Hospital Medical Center Primary Care offices serve as the medical home for over 33,000 children. The Pediatric Primary Care Center (PPCC), Hopple Street Health Center (HPC) and Fairfield Primary Care (FPC) serve an underserved population. Annually, these practices provide over 60,000 visits. Traditional outreach efforts in these offices have included reminder phone calls and/or texts when patients were overdue for well child care (WCC). These efforts were time and resource intensive, as they required personnel to manually complete and document attempts. Additionally, due to high resource needs to accomplish such efforts, there has been no outreach to those 6 years and older.

Numerous studies exist speaking to the efficacy of automated reminder (i.e. notifying parents of needed immunizations) and recall (i.e. notifying parents of overdue immunizations) systems, including text messaging systems.^{1,2,3} Other studies show that the combination of texting and calls proves even more successful in reaching patients.³ These systems are more cost effective and efficient. Differences in the timing of reminders to schedule, as well as the message itself, has been shown to make a difference in the outcomes of reaching patients or scheduling appointments.⁴ However, there remains a need for research that identifies the degree to which combinations of patient reminder systems improve outcomes, especially the outcome of on-time immunization, and how these approaches differ by age of child.¹

Following the COVID-19 pandemic shut-down in which thousands of well child appointments were cancelled or delayed, the importance of a systematic outreach process became more critical. The traditional process is non-standardized and the efficacy of the work is both unknown and expensive. Our objective is to determine the effectiveness of varied outreach methods (e.g. automated reminder calls/text messages with or without personalized calls/texts, MyChart messaging) to children age 12-14 months, 4 years old, or 6-17 years old who are due for a WCC visit and don't have one scheduled in the next 45 days on the outcomes of appointment scheduling, appointment completion, and receipt of the MMR vaccination.

2. Design/Method

To achieve our objective, we will conduct a 2×2 factorial randomized controlled trial. Randomization is justified because 1) it is a rigorous approach to answer our question and 2) we do not have the resources or appointment availability to personally contact every patient who is eligible and have them schedule immediately.

Patient Population:

Patients are eligible for inclusion in this study if they are in one of four eligible groups:

12-14 months AND	4 years AND

• doesn't have a well visit scheduled in the next 45 days• have not yet received 12-month immunizations• have English and/or Spanish as preferred language	
• doesn't have a well visit scheduled in the next 45 days• has not had a well child visit in 365 days• have English and/or Spanish as preferred language

6-11 years AND	12-17 years AND

• doesn't have a well visit scheduled in the next 45 days	
• doesn't have a well visit scheduled in the next 45 days

 • has not had a well child visit > 365 days • have English and/or Spanish as preferred language 	
 • has not had a well child visit in 365 days • have English and/or Spanish as preferred language
---	---

Factors under study (levels):

Personal Contacts (12-14 month & 4-year-olds) Trial:

Number of automated messages sent prior to any personal contact attempts (1 vs. 2)
Number of personal contact attempts made by medical assistant (0 vs. 1)

	1 automated message sent	2 automated messages sent
0 personal contact attempt		
1 personal contact attempt		

MyChart Trial:

Families enrolled in MyChart will be selected and randomized into the following groups:

	no message	1 MyChart message sent	2 MyChart messages (e.g. Mon and Thurs)
Low Tailored Message			
High Tailored Message			

Number of messages (0 vs. 1 vs. 2); Type of messages (low tailored message with name only vs. high tailored message with date of last WCC and age included)

Televox (age 6-11yo) Trial:

Patients will be randomized into the following three groups. Patients with MyChart are excluded:

no message	Low tailored Message 2 automated standard messages sent (e.g. Thu, Fri)	High Tailored Message 2 automated tailored messages sent (e.g. Thu, Fri)
-------------------	---	--

Televox (age 12-17yo) Trial:

Patients will be randomized into the following three groups:

no message	Low Tailored Message 2 automated tailored messages sent (e.g. Thu, Fri)	COVID Tailored Message 2 automated messages sent (e.g. Thu, Fri)
-------------------	---	--

Automated Message: Parents indicate their preferred mode of reminder (e.g. call or text message) when they schedule appointments. Cincinnati Children's uses a HIPAA compliant platform called TeleVox to send automated calls and text reminders to parents according to their preferences which are recorded in the Electronic Health Record (EHR).

Here is the script for **low tailored automated messages** that will be sent via call or text:

Clinic	Message 1*	Message 2*
HPC	Hi! Hopple misses you! (INSERT FIRST NAME) is due for a checkup. Please call [contact], option 1 to schedule a visit as soon as possible.	Hi! If you haven't already, please call [contact], option 1 to schedule (INSERT FIRST NAME)'s upcoming visit at Hopple.
FPC	Hi! Fairfield misses you! (INSERT FIRST NAME) is due for a checkup. Please call [contact], option 1 to schedule a visit as soon as possible.	Hi! If you haven't already, please call [contact], option 1 to schedule (INSERT FIRST NAME)'s upcoming visit at Fairfield.
PPC	Hi! PPC misses you! (INSERT FIRST NAME) is due for a checkup. Please call [contact], option 1 to schedule a visit or walk in today.	Hi! If you haven't already, please call [contact], option 1 to schedule (INSERT FIRST NAME)'s upcoming visit at PPC or walk in today.

*Message Scripts have been translated into Spanish by Interpreter Services

This is the script for **high tailored automated messages** that will be sent via call or text:

Clinic	Message 1*	Message 2*
HPC	(INSERT FIRST NAME) was seen for a checkup at Hopple on XX/XX/XXXX & is due for a (INSERT CURRENT AGE) checkup. Please call [contact] opt 1.	If you haven't, please call [contact] opt 1 to schedule (INSERT FIRST NAME)'s (INSERT CURRENT AGE) checkup at Hopple. Stay up to date!
FPC	(INSERT FIRST NAME) was seen for a checkup at Fairfield on XX/XX/XXXX & is due for a (INSERT CURRENT AGE) checkup. Please call [contact] opt 1.	If you haven't, please call [contact] opt 1 to schedule (INSERT FIRST NAME)'s (INSERT CURRENT AGE) checkup at Fairfield. Stay up to date!
PPC	(INSERT FIRST NAME) was seen for a checkup at PPC on XX/XX/XXXX & is due for a (INSERT CURRENT AGE) checkup. Please call [contact] opt 1 to schedule or walk in today.	If you haven't, please call [contact] opt 1 to schedule (INSERT FIRST NAME)'s (INSERT CURRENT AGE) checkup at PPC or walk in today. Stay up to date!

This is the script for **COVID tailored automated messages** that will be sent via call or text:

Clinic	Message 1*	Message 2*
HPC	Hi! Hopple misses you! (INSERT FIRST NAME) is due for a checkup. Please call [contact], option 1 to schedule a visit as soon as possible. COVID vaccine is available if interested.	Hi! If you haven't already, please call [contact], option 1 to schedule (INSERT FIRST NAME)'s upcoming visit at Hopple. COVID vaccine is available if interested.
FPC	Hi! Fairfield misses you! (INSERT FIRST NAME) is due for a checkup. Please call [contact], option 1 to schedule a visit as soon as possible. COVID vaccine is available if interested.	Hi! If you haven't already, please call [contact], option 1 to schedule (INSERT FIRST NAME)'s upcoming visit at Fairfield. COVID vaccine is available if interested.
PPC	Hi! PPC misses you! (INSERT FIRST NAME) is due for a checkup. Please call [contact], option 1 to schedule a visit or walk in today. COVID vaccine is available if interested.	Hi! If you haven't already, please call [contact], option 1 to schedule (INSERT FIRST NAME)'s upcoming visit at PPC or walk in today. COVID vaccine is available if interested.

*Message Scripts have been translated into Spanish by Interpreter Services

Personal Contact Attempts: Medical assistant(s) will use the following message/script to personally contact families via text message and then phone call.

Clinic	Text Message*	Call Script*
--------	---------------	--------------

Outreach Methods Study Protocol & SAP

Version 1.1, 1/14/22

pg. 5

HPC	Hi, this is [Staff First Name] from Hopple St. Health Center. [Pt first name] is due for a check up. I'll call in a day or two to help schedule that appointment or you can call [contact], option 1 to schedule.	Hi, this is [Staff First Name] from Hopple St. Health Center. I noticed that [Child's First Name] is due for a check up. Can I schedule that for you right now? Alternate script for leaving a voice message: Hi, this is [Staff First Name] from Hopple St. Health Center. I noticed that [Child's First Name] is due for a check up. Sorry I missed you. Please call [contact], option 1 to schedule your appointment.
FPC	Hi, this is [Staff First Name] from Fairfield. [Pt first name] is due for a check up. I'll call in a day or two to help schedule that appointment or you can call [contact], option 1 to schedule.	Hi, this is [First Name] from Fairfield. I noticed that [Child's First Name] is due for a check up. Can I schedule that for your right now? Alternate script for leaving a voice message: Hi, this is [First Name] from Fairfield. I noticed that [Child's First Name] is due for a check up. Sorry I missed you. Please call [contact], option 1 to schedule your appointment.
PPC	Hi, this is [Staff First Name] from PPC. [Pt first name] is due for a check up. I'll call in a day or two to help schedule that appointment or you can walk in today to have your child seen! You can also call [contact], option 1 to schedule.	Hi, this is [First Name] from PPC. I noticed that [Child's First Name] is due for a check up. Can I schedule that for your right now? Alternate script for leaving a voice message: Hi, this is [First Name] from PPC. I noticed that [Child's First Name] is due for a check up. Sorry I missed you. Please call [contact], option 1 to schedule your appointment or walk in today to have your child seen.

*Scripts have been translated into Spanish versions by Interpreter Services

Response variables (outcomes):

- Appointment **was scheduled** within 2 weeks of intervention (Y/N) (date of actual appointment may be greater than 2 weeks from intervention)
- Appointment **was completed** within 8 weeks of intervention (Y/N). Appointment completed within 8 weeks of randomization will be used for group who does not receive any intervention.
- (Primary Outcome) Receipt of MMR by 15 months of age or receipt of 2nd MMR dose by 3 months after randomization (Y/N)
- Receipt of 1st COVID vaccination (ages 12-17 years) within 8 weeks of first intervention (Y/N)
- Family member receipt of COVID vaccination in our health system within 8 weeks of first intervention

Blocking: (controlling for factors that might influence the outcome)

- Age (12-14 months, 4 years)
- Clinic location (PPC, HPC, FPC)

Personal Contacts (12-14 months & 4-year-olds) Trial:

Randomization: Eligible patient will be identified by running a report in the electronic health record (EHR). We will run this report, stratified by clinic location, and randomly assign patients into one of the four groups created by our 2 X 2 design. Groups will receive their assigned intervention in one of four successive weeks with the sequence randomly assigned (see table below).

Replication: We will conduct a total of 3 trials, repeating the randomization procedure every 4 weeks to identify children who become eligible: Weeks 1-4 = trial #1, weeks 5-8 = trial #2, weeks 9-12 = trial #3.

Outreach Methods Study Protocol & SAP

Version 1.1, 1/14/22

	1 automated message sent	2 automated messages sent
0 personal contact attempt	Message sent on Thu (weeks 3, 5, 10)	Message sent on Thu & Fri (weeks 4, 6, 12)
1 personal contact attempt	Above plus attempt Mon – Fri of following week (weeks 2, 7, 11)	Above plus attempt Mon – Fri of following week (weeks 1, 8, 9)

MyChart and Televox Trials (6-17 years old):

Randomization: Eligible patients will be identified by running a report in the electronic health record (EHR). We will run this report, stratified by clinic location, and randomly assign patients into one of the study groups as described above. Groups will receive their assigned intervention in one of four successive weeks with the sequence randomly assigned (see table below).

We will randomize children who are eligible and implement interventions for each trial : Weeks 1-3 = Televox Trial 12-17yo, Weeks 4-7 = Televox Trial 6-11yo, Weeks 8-10 = MyChart Trial.

MyChart Trial:

	no message	1 MyChart message sent	2 MyChart messages (e.g. Mon and Thurs)
Standard Message	No intervention	Week A	Week B
Tailored Message		Week A	Week B

Televox (6-11yo) Trial:

no message	Low Tailored Message 2 automated standard messages sent (e.g. Thu, Fri) (weeks C, C)	High Tailored Message 2 automated tailored messages sent (e.g. Thu, Fri) (weeks D, D)
-------------------	--	---

Televox (12-17yo) Trial:

no message	Low Tailored Message 2 automated tailored messages sent (e.g. Thu, Fri) (week A)	COVID Tailored Message 2 automated messages sent (e.g. Thu, Fri) (week B)
-------------------	--	---

Of note, automated messages and/or personal contact attempts will not be completed if the parent schedules an appointment after being randomized but before receiving the intervention.

Covariates for logistic regression: (factors that might influence the outcome if not balanced across groups)

1. Child age at the time of randomization (rationale: visits are less frequent for children age 4 years)
2. Parent preference for call vs. text mode of contact (rationale: calls may be more likely to get blocked than texts)
3. Parent with activated MyChart account (Y/N) (rationale: not dependent on calling scheduling center to make appointment)

4. Access to appointment: Number of days to 3rd next available appointment at patient's clinic at time their first automated message is sent
5. Patient receipt of any past immunizations (Y/N) (rationale: vaccine refusing parents will be unlikely to change even if they return for well child check)
6. School-age vs. adolescent patient age (rationale: adolescents less likely to get yearly check-ups)
7. Historical no-show rate
8. Community rates of COVID based on 7 day moving average.

Power/Sample Size

Personal Contacts (12-14 month & 4-year-olds) Trial:

We based our hypotheses (see table, below) on a systematic review's pooled estimates of effect size for automated messages and personalized calls finding 37% and 40% of children, respectively, completed immunizations.¹ Because of the significant cost involved in making personal contacts, the minimal difference in outcome that would make it worth the effort is high.

Hypotheses	% of children who receive MMR by 15 months of age	
	1 automated message sent	2 automated messages sent
0 personal attempts	20% ^C	35% ^B
1 personal attempt	50% ^A	65% ^{AB}

We calculated sample size needed per group to detect a difference for each of the contrasts below with alpha of 0.05 and power of 80%.

Contrast	Sample Size per Group
A vs C	36
B vs C	136
A vs. B	167
A vs. AB	167
B vs. AB	40
C vs. AB	16

To fully power the 2 X 2 factorial trial, we estimate needing 167 per group X 4 groups = 668 total subjects. There are currently 712 children eligible for the study. More will become eligible every month so we expect to far exceed the required sample size after 3 replications. If needed, we could increase the number of replications of the trial to reach the targeted sample size. We acknowledge that we are not powered to precisely estimate any interactions between interventions.

MyChart Trial:

In hypothesis testing for 0 message vs. 1 message vs. 2 messages, we will do the testing in a fixed sequence - test 2 messages vs. 0 message first, only if it is significant then test 2 messages vs. 1 message, thus the type I error rate of 0.05 is retained. Since the hypothesis testing of 2 messages vs. 0 message would be considered easier to achieve than the hypothesis testing of 2 messages vs. 1 message, the power analysis for this trial should be based on the design of (standard message vs. tailored message) by (1 message vs. 2 messages). We based our hypotheses (see table, below) on previous work indicating approximately 20% WCC appointment completion on automated text reminders. We anticipate that a tailored message increases the WCC appointment completion rate by another 10%.

Hypotheses		% of children complete WCC within 8 weeks

	No message	1 automated message sent	2 automated messages sent
Standard Message	2%	10% ^C	20% ^B
Tailored Message		20% ^A	30% ^{AB}

We calculated sample size needed per group to detect a difference for each of the contrasts below with alpha of 0.05 and power of 80%.

Contrast	Sample Size per Group
A vs C	199
B vs C	199
A vs. AB	293
B vs. AB	293
C vs. AB	62

We assume no difference between A vs. B and thus not consider powering the comparison between these two groups, but we will explore non-inferiority analysis for this comparison in data analysis. To fully power the above contrasts, we estimate needing 293 per group X 4 groups = 1172 subjects. Adding 293 in the zero message group, we would need a total of 1465 subjects. There are currently 1000 children eligible for the study. More will become eligible every month so we expect to exceed the required sample size after 2 replications. If needed, we could increase the number of replications of this trial to reach the targeted sample size. We acknowledge that we are not powered to precisely estimate any interactions between interventions.

Televox (6-11yo) Trial:

We calculated sample size based on the following hypotheses:

% of children complete WCC within 8 weeks		
no message	2 Low Tailored Messages	2 High Tailored Messages
2%	20%	30%

With alpha of 0.05 and power of 80%, to fully power the contrasts between the above groups, we need 293 per group X 3 groups=879 subjects. Currently there are 2500 kids eligible, so we expect to reach the targeted sample size.

Televox (12-17yo) Trial:

We calculated sample size based on the following hypotheses:

% of children complete WCC within 8 weeks		
no message	2 Low Tailored Messages	2 COVID Tailored Messages
2%	30%	40%

With alpha of 0.05 and power of 80%, to fully power the contrasts between the above groups, we need 356 per group X 3 groups=1068 subjects. Currently there are 1100 kids eligible, so we expect to reach the targeted sample size.

Analysis

We will conduct descriptive analyses to characterize the participants in terms of demographics and other potential covariates in consideration (child age group, parent's preference for call vs. text mode of contact, whether parent

Outreach Methods Study Protocol & SAP

Version 1.1, 1/14/22

pg. 9

had activated MyChart account, access to appointment, whether patient receipt of any past immunizations, historic no show rate, and community rates of COVID). We will use chi square tests to examine whether participants in the 4 groups are similar in these characteristics.

For the Personal Contact (12-14 mo & 4 years old) trials, we will conduct intent-to-treat analyses using logistic regression models (without adjusting for covariates) for each of our three binary outcomes: completed appointment within 2 weeks, completed appointment within 8 weeks, receipt of MMR by 15 months of age or receipt of 2nd MMR by 3 months after randomization. We will do pair-wise comparison among the 4 groups and adjust p value of each comparison for multiplicity. If participants in the 4 groups differ on potential covariates, we will conduct additional analyses adjusted for these variables.

For the MyChart and Televox Trials (6-17 years old), we will conduct intent-to-treat analyses using logistic regression models (without adjusting for covariates) for each of the binary outcomes: scheduled appointment within 2 weeks, completed appointment within 8 weeks, receipt of 1st dose of COVID vaccination (age 12-17 years) within 8 weeks, family member receipt of COVID vaccination within 8 weeks. We will do pair-wise comparison among the treatment groups and adjust p value of each comparison for multiplicity. If participants differ in potential covariates across treatment groups, we will conduct additional analyses adjusted for these variables. We will explore non-inferiority analysis for comparison the two groups that are expected to have similar appointment scheduled and completion rate in the MyChart trial.

We will also conduct per-protocol analyses according to the interventions actually received by the participants, recognizing that actual intervention received could be different from initial randomized intervention. For example, a parent allocated to group A might schedule an appointment after receiving the automated message and therefore would not receive a personalized contact attempt. In addition, we may explore potential interaction between the two interventions as a secondary analysis. All analysis will be conducted using SAS version 9.4.

Duration

The study will begin upon IRB approval and continue through December 31, 2022. During this time, we will discuss the significance of data, potential future projects and dissemination of results.

Process of Obtaining Consent

For this study, we request a waiver of consent due to the minimal risk to participants involved. Given the population we are attempting to contact using the various outreach methods has missed appointments, it would not be possible to obtain prospective consent. That said, we will honor parent preferences for how they receive automated messages. Collected data about appointment attendance and MMR vaccination status is already being documented in the EHR, and the collection of data will not affect the rights and welfare of subjects.

We request waiver of consent such that there is (1) potential, minimal, risks to the participant (see below), (2) de-identification of PHI, and (3) participation in the study will not affect current/future care received through CCHMC.

All identifying information will be removed once data collection is complete. Data will be kept securely on a CCHMC computer that is password protected. Any hard copies of data will be locked in a private office.

Facilities and Performance Sites

Data analysis will be done on the Main Campus of CCHMC and at the CCHMC primary care offices (PPCC, HPC, FPC, and SBHCs).

Potential Benefits

The results of this study will aid CCHMC pediatric primary care centers in improving and redesigning an outreach system to children behind on necessary preventative services who have gaps in needed primary care. It will identify the most effective ways to reach, engage, and schedule patients for care when appropriate. This will enable the primary care offices to allocate the appropriate amount of resource to outreach efforts moving forward, ensuring high risk children receive reminders for care.

Potential risks, discomforts, inconveniences, and precautions

Outreach Methods Study Protocol & SAP

Version 1.1, 1/14/22

pg. 10

The only significant risks are breach of confidentiality and potential discomfort/inconvenience associated with receiving texts or phone calls indicating that care gaps exist for a child. As noted above, personal health information (PHI) will be obtained via the electronic medical record. After obtaining this information, patients will be de-identified in the created database and securely stored.

Risk/Benefit analysis

While immediate benefit to any given individual or family is unknown, this study involves minimal risk.

Cost of Participation

There is no cost for participation.

Payment for Participation

There is no reimbursement for participation.

Request for HIPAA Waiver

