1.2 Outcome measures

Primary

- Adolescent well-care visit completed within 8 weeks of receiving first intervention
 - Appointment completed (yes or no) based on electronic health record documentation

Secondary

- Adolescent well-care visit scheduled within 2 weeks of receiving first intervention
 - Appointment scheduled (yes or no) based on electronic health record documentation
- Adolescent receipt of COVID-19 vaccine within 8 weeks of receiving first intervention
 - COVID-19 vaccine administered (yes or no) based on electronic health record documentation
- Family member receipt of COVID-19 vaccine within 8 weeks of receiving first intervention
 - COVID-19 vaccine administered (yes or no) based on electronic health record

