2.3.2 Primary outcome analysis

Primary outcome: Adolescent well-care visit completed within 8 weeks of first message sent or date of randomization for the control group.

- Appointment completed (yes or no) based on electronic health record documentation

For the primary outcome, we will use a logistic regression model to examine appointment completion within 8 weeks among the three randomized groups. If participants differ in potential covariates across treatment groups, we will conduct additional analyses adjusted for these variables.

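### The 45-day booking screen stops short of the 8-week completion window, so some visits booked before randomization count as successes, over more days in message arms than in controls.

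*Combined protocol and SAP*

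**What the plan says.** **Eligibility.** Under Patient Population in protocol section 2, each of the four age groups requires that the child "doesn't have a well visit scheduled in the next 45 days". Nothing is said about visits booked further ahead.

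**Completion window.** The protocol's list of response variables counts a completed appointment for 8 weeks from the intervention and adds: "Appointment completed within 8 weeks of randomization will be used for group who does not receive any intervention". SAP 2.3.2, for the 12-17 trial, gives the primary outcome as "Adolescent well-care visit completed within 8 weeks of first message sent or date of randomization for the control group".

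**Ascertainment.** SAP 1.2 defines it as "Appointment completed (yes or no) based on electronic health record documentation". Neither document sets a condition on the booking date.

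**Timing of messages.** For the Personal Contacts trial, and again for the MyChart and Televox trials, the protocol says: "Groups will receive their assigned intervention in one of four successive weeks with the sequence randomly assigned". Their calendar is "Weeks 1-3 = Televox Trial 12-17yo, Weeks 4-7 = Televox Trial 6-11yo, Weeks 8-10 = MyChart Trial".

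**Bookings before the message.** The only rule is that messages and contacts "will not be completed if the parent schedules an appointment after being randomized but before receiving the intervention". It does not cover a booking that already existed at randomization.

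**The concern.** Eight weeks is 56 days, so the screen ends 11 days before the outcome window does, even in the control group. A child already booked for day 50 can be randomized, keep that visit and be scored as a success, although no message led to the booking.

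Two consequences need to be kept apart. Over the 11 days common to all arms, randomization balances these visits; they blur the contrasts without favouring an arm. In message arms the window also closes later, by the delay between randomization and first message. Randomization balances who holds an early booking, but not how many of those bookings each arm's window can reach. This could add to the message-versus-control difference in the MyChart trial and both Televox trials, and completion is the SAP's primary outcome for ages 12-17.

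The Personal Contacts trial is touched less. It has no no-message arm and its primary outcome is MMR receipt, so only its secondary completion outcome is exposed, through the arms' different weekly slots.

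**Working it through.** **1. The plan's own sample sizes.** The inputs, from the protocol's Power/Sample Size section, are 20% vs 30% (ages 6-11) and 30% vs 40% (ages 12-17), alpha 0.05 (taken as two-sided) and power 80%. With p the mean of the two rates,

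n = [1.96 √(2p(1−p)) + 0.842 √(p₁(1−p₁) + p₂(1−p₂))]² / (p₂−p₁)²

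- 20% vs 30%: 293.2 per group (plan: 293).
- 30% vs 40%: 355.9 per group (plan: 356).

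Both reproduce, and each gives 80% power.

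**2. Exposed days.** Take day 0 as the EHR report and randomization, and let the first message go out on day d. A visit booked before day 0 passes the screen from day 46.

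- Controls: 56 − 45 = 11 days.
- Message arm: (56 + d) − 45 = 11 + d days, so 14, 21 and 28 at d = 3, 10 and 17.

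The documents do not give d. These values are assumptions, one for a send in each of the first three weeks.

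**3. Dilution from the shared 11 days.** Let f be the share of children holding a visit on days 46-56, and assume 70% keep it. If messages do not affect those children, a planned rate p becomes (1−f)p + 0.7f. The documents do not give f, but they limit it: the planned no-message rate is 2% for all completions, so 0.7f ≤ 2% and f ≤ 0.02/0.7 = 2.9%.

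| f | 20 vs 30% becomes | Power, 293 per group | 30 vs 40% becomes | Power, 356 per group |
|---|---|---|---|---|
| 0 | 20.0 vs 30.0% | 80% | 30.0 vs 40.0% | 80% |
| 1% | 20.5 vs 30.4% | 79% | 30.4 vs 40.3% | 79% |
| 2% | 21.0 vs 30.8% | 77% | 30.8 vs 40.6% | 78% |
| 2.9% | 21.4 vs 31.1% | 76% | 31.1 vs 40.9% | 77% |

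This bound concerns the shared days only. The extra d days would add some further dilution to contrasts between two message arms.

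**4. Net excess in message arms.** Assume 0.2% of children hold a visit on each day beyond day 45 and 70% keep it, which is 0.14 points per day. Controls gain 0.14 × 11 = 1.5 points, within the 2% limit. A message arm gains 0.14 × (11 + d), so the difference is 0.14 × d.

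| d | Message arm gain | Control gain | Net excess |
|---|---|---|---|
| 3 | 2.0 | 1.5 | 0.4 points |
| 10 | 2.9 | 1.5 | 1.4 points |
| 17 | 3.9 | 1.5 | 2.4 points |

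Two message arms sent one week apart would differ by 0.14 × 7 = 1.0 point, against a planned 10-point difference between message types.

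**5. Personal Contacts slots.** Counting each arm's week within its 4-week block from the protocol's table:

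- One message, no contact: slots 3, 1, 2 (mean 2.0).
- Two messages, no contact: slots 4, 2, 4 (mean 3.3).
- One message, one contact: slots 2, 3, 3 (mean 2.7).
- Two messages, one contact: slots 1, 4, 1 (mean 2.0).

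The send delay therefore does not average out across these arms.

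**The case against.** The case for leaving the plan alone has real force.

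- **Balance.** Pre-booked visits on days 46-56 occur in every arm and do not bias a comparison. This stands; only the d extra days are at issue.
- **Offsetting loss.** A clock that starts at the message also drops visits made between randomization and the message, such as walk-ins or short-notice bookings. This stands, so the excesses above are before that offset. The screen makes pre-booked visits unlikely in that interval, so I regard the offset as partial, but its size is unknown.
- **Messages can act on booked families.** The scripts urge an early visit, and at PPC a walk-in. A family booked for day 50 may come sooner or be likelier to attend. This stands: these visits are not wholly beyond the reach of outreach, and step 3 is a pessimistic calculation.
- **Possible double counting.** The planned percentages are for any completion within 8 weeks and may already include such visits. If so, the dilution is smaller than shown.
- **Size of the planned effects.** They are 18 and 28 points over control in the 6-11 trial and the SAP, and 28 and 38 in the protocol's 12-17 hypotheses. An excess of 0.4 to 2.4 points would not overturn them.

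A reader might infer that power falls to 75% or lower. That needs f of 5% or 10%, which adds 3.5 or 7 points and exceeds the 2% that the plan allows for all control completions. A reader might also take the full 2.9 or 3.9 points in a message arm as bias, but controls gain 1.5 of them.

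**Conclusion.** The gap is real and nothing in either document closes it: a plan followed as written counts some visits booked before randomization, over 11 days in controls and 11 + d days in message arms. Within the plan's own 2% control rate, the shared days cost at most about 4 points of power (80% to 76%) at 293 per group and about 3 (80% to 77%) at 356. The net credit to a message arm is about 0.4 to 2.4 points for delays of 3 to 17 days, before the offset from visits made ahead of the message. That is small beside the planned effects over control. It is comparable to the whole assumed control rate, so it would matter if the true effects proved small.

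These sizes rest on an assumed 70% attendance, an assumed 0.2% of children per day and assumed delays. The documents supply none of them. They do not support the reading that a message-versus-control result would be an artefact, or that the Personal Contacts primary outcome is affected. Severity: moderate.

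**What to change.** **Trials or replications not yet randomized.** Change the EHR report, in all four age groups, to require no well visit scheduled within 56 days plus the longest planned send delay, or no future well visit at all. Count completion from randomization in every arm. The longer screen also protects any analysis that keeps the message-based window. State the planned delay in days for each arm.

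**The 12-17 trial.** SAP 2.2.1 puts its end at 8/5/21, so the screen can no longer be changed. Keep the as-allocated primary analysis. Add to SAP 2.3.2 a sensitivity analysis that excludes, in all three arms, children whose well visit was booked before randomization, identified by the EHR booking date. That date is fixed before allocation, so the exclusion is the same rule in each arm. Label the analysis as added after follow-up ended.

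**Cost.** One change to a report, one change of clock and one SAP sentence. A common clock leaves message arms d fewer days after the message, which is the price of equal windows. The eligible pool shrinks somewhat. This matters most in MyChart, which has 1000 eligible against 1465 needed, and in Personal Contacts, which has 712 against 668, a margin of 44 children (44/712 = 6.2%). The protocol already allows further replications in both.
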